5.3. PER PROTOCOL ANALYSIS SET (PP)

In order to assess the robustness of the efficacy analysis, the analysis of the efficacy end-point will be repeated on the Per Protocol (PP) analysis set. The Per-protocol analysis set will include all ITT patients who receive at least 14 daily doses without interruptions, and without any major deviation from the protocol procedures.

5.3.1. PROTOCOL DEVIATIONS

Protocol deviations to be reviewed will include, but will not be limited to, patients who:

- Did not meet inclusion/exclusion criteria or eligibility not adequately verified.
- Received disallowed concomitant medications pre- and/or post-treatment.
- Developed withdrawal criteria but were not withdrawn.

According to Quintiles SOPs the PDs are classified as Minor, Major and Critical. Starting from 1st March 2016, the categorization changed into Minor, Important (for Major) and Priority (for Critical).

In order to comply with the Protocol requirements, the categorization of 'Critical', 'Important' and 'Priority' will fall into the 'Major' one.

A. Major protocol deviations to be reviewed will include, but will not be limited to, the following groups:

1. Entry criteria:

- Any "no" response to inclusion criteria and/or any "yes" response to exclusion criteria and patient was subsequently enrolled.

NOTE: only in case of previous written Sponsor authorization this type of deviation can be considered

Document: PPD

Author: PPD

Version Number:

V2.2

Version Date:

21 March 2018

Template No: CS_TP_BS016 – Revision 3

Reference: CS_WI_BS005

Effective Date: 01May2012

Copyright © 2012 Quintiles Transnational Corp. All rights reserved.

The contents of this document are confidential and proprietary to Quintiles Transnational Corp. Unauthorized use, disclosure or reproduction is strictly prohibited.

as 'Minor'.

2. Investigational Medicinal Product:

- Investigational Product dosing error: in case the patient takes a dose of IP that is different from the assigned dose (example: dose level, DL0, DL1, DL6 or MTD as defined at the end of study Part A).
- Enrolled out of DL - NOTE: only in the case of previous written Sponsor authorization to have the patient enrolled on cohort DL0 this is not considered as a protocol deviation.
- Part A (between C2D1 and C6D28) and Part B: Non-compliant with IMP usage (under 80%). According to the protocol "A patient will be considered sufficiently compliant with Givinstat treatment if he/she has taken at least 80% of the prescribed dose over the total duration of study drug dosing".
- The site dispensed the used IMP stored out of the following storage conditions described in the IMP handling manual, to the patient without the Sponsor's written authorization: (i) IMP storage temperature $\geq 30^{\circ}\text{C}$ and $\leq 40^{\circ}\text{C}$ for ≥ 30 days, or (ii) IMP storage temperature $> 40^{\circ}\text{C}$
- Incorrect IMP dispensation to a patient: (i) in case the site incorrectly assign a dosage different from the one approved by the Sponsor at the time of enrollment (example: dose level, DL0, DL1, DL6 or MTD as defined at the end of study Part A), or (ii) in case the site performed a dose escalation not predicted by the study protocol.

3. Informed Consent:

- Patient did not sign Main ICF.
- ICF is signed after study procedure was done, except for invasive procedures performed before the ICF signature as clinical practice AND, anyway, only after the Sponsor's written authorization to be obtained before the first drug intake.

4. Concomitant Medications:

- Patient used prohibited medication(s) during the study course.

5. Study Procedures:

- SAEs not reported in according to the correct timelines.

Document: PPD

Author: PPD

Version Number:

V2.2

Version Date:

21 March 2018

Template No: CS_TP_BS016 – Revision 3

Reference: CS_WI_BS005

Effective Date: 01May2012

Copyright © 2012 Quintiles Transnational Corp. All rights reserved.

The contents of this document are confidential and proprietary to Quintiles Transnational Corp. Unauthorized use, disclosure or reproduction is strictly prohibited.

B. Minor protocol deviations to be reviewed will include, but will not be limited to, the following groups:

1. Entry criteria:
 - Patient enrolled without all data and results available to evaluate the inclusion and exclusion criteria, or not following the correct enrollment protocol procedures.
 - Enrollment of the patient with the local laboratory report for confirming the JAK2^{V617F} positivity before receiving the confirmation from the central laboratory and without the Sponsor's written authorization.
2. Investigational Medicinal Product:
 - The patient has assumed the IMP out of the procedures described in the IMP Handling manual.
 - IMP accountability not done or not fully completed by the site.
 - Missed IMP dose that does not affect the 80% of IMP compliance.
3. Visit Schedule:
 - Screening visit performed outside approved protocol window (28 days +/- 7 days). In fact, patient must be medically stable on the basis of physical examination, medical history, and vital signs performed at screening [within 28 days before randomization to Day 1]. If there are abnormalities, they must be consistent with the underlying illness in the study population.
 - End of Study Visit (EOS) not performed or performed more than 7 days after last drug intake, except for completers patients.
 - Patient visits performed outside approved window, except in case of the Sponsor's written authorization (for example, the patient is in vacation and the study visit should be performed 2 days before his/her coming back).
 - Patient visits not fully performed as per study protocol.
 - Patient(s) miss an entire visit.
4. Informed Consent:
 - Incorrect version of ICFs signed.
 - In case of pregnancy, the patient – if female – or the patient partner – if the patient is a male - has not signed the Pregnancy ICF and the pregnancy data have been collected.
 - Missing date of ICFs.
 - Site personnel who signed ICFs is not on Site Personnel Signature Delegation Log and/or not authorized by PI to sign ICFs.
 - Bone Marrow (BM) consent not provided, but BM histological evaluation done.
 - Pregnant Partner ICF obtained although the partner of the patient IS not pregnant.
 - Latest version of non-substantial ICFs not signed by the patient at the first study visit

Document: PPD

Author: PPD

Version Number:

V2.2

Version Date:

21 March 2018

Template No: CS_TP_BS016 – Revision 3

Reference: CS_WI_BS005

Effective Date: 01May2012

Copyright © 2012 Quintiles Transnational Corp. All rights reserved.

The contents of this document are confidential and proprietary to Quintiles Transnational Corp. Unauthorized use, disclosure or reproduction is strictly prohibited.

once the ICFs is available at site.

- IEC/IRB contact details or site's contact details not included on ICFs.
- Patient did not directly add his/her name on the ICFs space near to the signature.

5. Study Procedures:

- Lack of adherence to delegation requirements.
- Bone Marrow consent provided, but sample not collected by the site.
- SAEs not appropriately reported Systemic lack of Principle Investigator oversight of safety data.
- Not collecting samples related to primary efficacy variables: haematology samples not collected at cycle 3.
- Study procedures needed for the primary objectives and primary endpoints not done: haematology samples not collected, spleen evaluation not done, MPN-SAF QOL and Questionnaire not completed at all at cycle 3, ECG including QTc determination not completed at cycle 3. Study procedures needed for the secondary objectives and secondary endpoints not done: haematology samples not collected, spleen evaluation not done, MPN-SAF QOL Questionnaire not completed at all, PK sample not collected at cycles 3 and 6 and Bone Marrow histological evaluation not done at cycle 6.
- Study procedures needed for the exploratory objectives and endpoints not done: haematology samples not collected, PD samples not collected, spleen evaluation not done, MPN-SAF QOL Questionnaire not completed at all, JAK2^{V617F} not collected according to the protocol and Bone Marrow histological evaluation not done.
- A negative urine B-human chorionic gonadotropin (B-hCG) pregnancy test not collected at screening visit for patient, if women of childbearing potential.
- Delegation log not up to date prior to study procedures being performed.
- Study procedures that do not affect the patient's safety, eligibility confirmation and response assessment not done.
- Patient did not answer to all the questions of the MPN-SAF QOL Questionnaire. Information partially collected.

6. Laboratory:

- Back-up sample of JAK2^{V617F}, PK and PD not collected.
- Primary and back-up samples of JAK2^{V617F}, PK and PD of the same patient and collected at the same visit, shipped to the Central Laboratory with the same shipment.
- PK and/or PD samples not collected at pre-dose at visit Day1 Cycle 1 and at the subsequent time points as predicted by the protocol.
- Blood samples drawn by staff not listed on study delegation log or site staff not certified.

Document: PPD

Author: PPD

Version Number:

V2.2

Version Date:

21 March 2018

Template No: CS_TP_BS016 – Revision 3

Reference: CS_WI_BS005

Effective Date: 01May2012

Copyright © 2012 Quintiles Transnational Corp. All rights reserved.

The contents of this document are confidential and proprietary to Quintiles Transnational Corp. Unauthorized use, disclosure or reproduction is strictly prohibited.

All potential protocol deviations will be discussed and reviewed on a case-by-case basis before the database lock.

Individual protocol deviations will be presented in a data listing. The number and percentage of patients with protocol deviations will be summarized by deviation. Additional Major and Minor protocol deviations may be identified during data review and will be reflected in the table and listing as appropriate.

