5. ANALYSIS SETS

Agreement and authorization of patients included/excluded from each analysis set will be conducted prior to the database lock of the study during the Data Review Meeting.

The analysis sets are defined distinctly for each of the 3 planned analyses.

The number and percentage of the patients included in the analysis populations will be reported in a table showing the reason of exclusion for all patients enrolled into study. A listing of reasons of exclusion from analysis population will be provided.

Patients who sign an informed consent form but who do not start Study treatment for any reason, will be considered as “Screening Failures”. For these patients, a separate Table will be produced including the primary reason for screen failure and patient’s demographic information as per electronic CRF.

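### Late SAE reporting by a site counts as a Major deviation and so excludes the patient from the Per Protocol set, which may bias the robustness check of the Part B response rate

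*SAP*

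**What the plan says.** SAP section 5.3 gives the purpose of the PP analysis as "In order to assess the robustness of the efficacy analysis". It restricts the set to ITT patients with at least 14 uninterrupted daily doses and "without any major deviation from the protocol procedures". The rule is not limited to deviations that could affect efficacy.

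Section 5.3.1 then defines Major. It folds the CRO's higher grades into one class: "the categorization of 'Critical', 'Important' and 'Priority' will fall into the 'Major' one". Under Major, the only entry in the study procedures group is "SAEs not reported in according to the correct timelines".

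Two items in the Minor list matter here:

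- "SAEs not appropriately reported Systemic lack of Principle Investigator oversight of safety data", which also concerns SAE reporting.
- "Study procedures needed for the primary objectives and primary endpoints not done: haematology samples not collected, spleen evaluation not done", which concerns the Cycle 3 data behind the primary endpoint.

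On review, section 5.3.1 says "All potential protocol deviations will be discussed and reviewed on a case-by-case basis before the database lock", and section 5 says that agreement on who enters each set "will be conducted prior to the database lock of the study during the Data Review Meeting". Section 17.2 evaluates the Part B primary efficacy parameters on both ITT and PP.

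**The concern.** A PP set is useful as a robustness check if it removes patients whose treatment or assessment departed from the plan in a way that could distort the response rate. Late SAE reporting does not do that. It reflects how quickly site staff filed a form, and tells us nothing about whether the patient was eligible, took the drug, used prohibited medication or was assessed correctly.

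The deviation also cannot occur in a patient without an SAE. The exclusion therefore selects on an event that happens after treatment starts and that may be related to response. Section 5.2 keeps patients who drop out for drug-related TEAEs before the efficacy assessment in ITT as No Response. If such a patient's event was an SAE reported late, PP removes a non-responder whom the ITT definition was written to retain. Agreement between PP and ITT would then be less informative than it appears.

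**Working it through.** **Step 1. Does the text lead to exclusion?** Section 5.3 removes any ITT patient with a Major deviation. Section 5.3.1 lists late SAE reporting as Major and attaches no exception. Other Major items do carry one: entry criteria, enrolment at DL0, storage temperature and consent timing can each be excused by written Sponsor authorization. Read together, the two sections put a patient with a late-reported SAE outside PP.

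**Step 2. Could this be the only reason for exclusion?** Yes. The other PP conditions are 14 uninterrupted daily doses (5.3) and compliance of at least 80% (5.3.1). For a patient who stops permanently, section 15.1 calculates compliance up to the withdrawal date. A patient who takes the drug properly for several weeks, has an SAE and stops can meet both conditions and still be lost because the report was late.

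**Step 3. Is the classification consistent with the purpose of PP?** Missing Cycle 3 haematology, spleen or symptom assessments are Minor, so they do not exclude from PP through the deviation rule. Section 5.2 does remove some such patients from ITT, but only when haematocrit does not settle the response and at least two of four assessments are missing. A late safety report, which has no bearing on response, excludes outright.

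**Step 4. The plan's own design figures.** Section 3.5 specifies 12 patients in Stage 1 (stop at 6 or fewer responders) and 28 in total (18 or more responders reject the null). The probability of rejecting the null is the sum over x = 7 to 12 of P(X1 = x) × P(X2 ≥ 18 − x), with X1 binomial on 12 and X2 binomial on 16.

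| Quantity | SAP 3.5 | Recomputed |
|---|---|---|
| Rejection probability, RR = 0.50 | 0.081 | 0.0815 |
| Rejection probability, RR = 0.75 | 0.902 | 0.9017 |
| Early termination, RR = 0.50 | 0.613 | 0.6128 |
| Expected N, RR = 0.50 | 18.2 | 18.20 |

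The figures reproduce, and none of them depends on PP.

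**Step 5. How far could PP move?** The SAP gives no number of late-reported SAEs, so k, the number of patients dropped for this reason alone, is assumed to be 1 to 4. ITT is assumed to hold all 28 patients with 18 responders, the final decision bound: 18/28 = 64.3%. Dropping k non-responders gives 18/(28 − k). Dropping k responders gives (18 − k)/(28 − k).

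| k | All dropped are non-responders | All dropped are responders |
|---|---|---|
| 1 | 18/27 = 66.7% | 17/27 = 63.0% |
| 2 | 18/26 = 69.2% | 16/26 = 61.5% |
| 3 | 18/25 = 72.0% | 15/25 = 60.0% |
| 4 | 18/24 = 75.0% | 14/24 = 58.3% |

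**Step 6. Expected shift.** Let p be the response rate in ITT, f the share of ITT patients dropped for this reason alone, and q the response rate among those dropped. The expected PP rate is (p − f·q)/(1 − f), so the shift is f·(p − q)/(1 − f). Take p = 0.60 as an assumption:

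- f = 0.05 (for example, 10% with an SAE and half of those reported late), q = 0: 0.60/0.95 = 0.632, a shift of +3.2 points.
- f = 0.20 (an extreme case), q = 0: 0.60/0.80 = 0.750, a shift of +15 points.
- f = 0.20, q = 0.30: (0.60 − 0.06)/0.80 = 0.675, a shift of +7.5 points.
- q = 0.60: no shift at any f.

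The sign is that of p − q, so the rate falls if SAE patients respond better than average.

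**The case against.** The strongest defence is that exclusion is not automatic. Section 5.3.1 presents the Major items as deviations to be reviewed, requires case-by-case discussion before database lock, and leaves set membership to the Data Review Meeting. The Minor list also has an entry on SAEs not appropriately reported, although that line appears to run two items together. The text therefore does not settle that every late report ends up Major. This stands in part: review could prevent the problem. But no criterion is given for keeping a patient with a listed Major deviation in PP, and in an open-label study that discretion would be exercised with responses known.

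A second defence is overlap. Many SAE patients who interrupt or stop dosing may already fail the 14-dose or 80% compliance condition, so late reporting adds nothing for them. That is right for those patients, and it reduces the likely size of the effect. Step 2 shows that it does not remove it.

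A third is that PP is supportive. Section 5.2 assigns all efficacy analyses to ITT, and the Simon rule counts responders among 28 patients. This stands, although section 17.2 names PP beside ITT for the Part B primary endpoint.

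A reader might infer that PP is certain to be inflated, or that a PP rate passing 0.75 would change the trial's conclusion. The documents support neither. There is no count of late reports and no response rate in SAE patients. The value 0.75 is the hypothesised alternative in section 3.5; the final decision bound is 18 responders of 28.

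**Conclusion.** The point holds as a risk to a supportive analysis. As written, sections 5.3 and 5.3.1 let an administrative site failure, possible only in patients with an SAE, remove those patients from the PP check of the Part B response rate. Bias requires at least one late-reported SAE confirmed as Major in an ITT patient who has no other reason for exclusion, and a response rate in such patients that differs from the rest. An upward shift is more likely where SAE patients stop and are counted as No Response in ITT, but the direction is not established.

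If all 28 patients are in ITT with 18 responders, one or two exclusions move the PP rate by +2.4 or +4.9 points (non-responders dropped) or by −1.3 or −2.8 points (responders dropped). The ITT result, the Simon bounds, the type I error and the power are untouched.

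**What to change.** In section 5.3, state that only Major deviations affecting eligibility, study drug intake, prohibited medication or the response assessment exclude a patient from PP. In section 5.3.1, keep late SAE reporting in the deviation table and listing, flagged as not excluding from PP. With that change, the shift from this cause is zero.

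The SAP says that its Major mapping is made to comply with the protocol, and section 3.7 plans no change from the protocol other than software. The new wording should therefore be checked against the protocol's PP definition and, if it departs from it, recorded in section 3.7 as a change in planned analysis. The cost is a small wording change, one flag on the listing and possibly that check. No data collection or design figure changes.

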5.4. MAXIMUM TOLERATED DOSE ANALYSIS SET (MTD)

The MTD analysis set will include all patients who experienced DLTs in Cycle 1 of **Part A**, or who received at least 90% of the doses of study medication in Cycle 1 of **Part A**. The data regarding the Cycle 1 of **Part A** will be used to determine MTD from this analysis set.

5.5. PK ANALYSIS SET (PK)

The PK Analysis Set will consist of all SAF patients with at least 1 PK assessment.

This analysis set will be used for PK analysis.

6. GENERAL CONSIDERATIONS

6.1. REFERENCE START DATE AND STUDY DAY

Study Day will be calculated from the reference start date and will be used to show start/stop day of assessments and events.

For both **Part A** and **Part B**, reference start date is defined as the day of the first dose of study medication (C1D1 is the day of the first dose of study medication) and is referred to as “Day 1” for the definition of the Baseline value. Day - 1 is the day that precedes Day 1. Day 0 is not defined.

The date and the time of the first investigational study drug of each patient will be taken from the “On-site Dosing (DOSING)” raw data panel.

- *If the date of the event is on or after the reference date then:
Study Day = (date of start of the event – reference date) + 1.*
- *If the date of the event is prior to the reference date then:
Study Day = (date of start event – reference date).*

Document: PPD

Author: PPD

Version Number:

V2.2

Version Date:

21 March 2018

Template No: CS_TP_BS016 – Revision 3

Reference: CS_WI_BS005

Effective Date: 01May2012

Copyright © 2012 Quintiles Transnational Corp. All rights reserved.

The contents of this document are confidential and proprietary to Quintiles Transnational Corp. Unauthorized use, disclosure or reproduction is strictly prohibited.

In the situation where the event date is partial or missing, the date will appear partial or missing in the listings, and Study Day, and any corresponding durations will be presented based on the imputations specified in [Appendix 2](#); Partial Date Conventions.

The duration of an event will be presented in days, rounded to one decimal place and will be calculated as follows:

Duration of event= (date of end of event – date of start of event) + 1.

In the case of a retest (same visit number assigned) of a non laboratory data (i.e. 3 ECG repeated as per QTc prolongation), the average of all measurements will be used for by-visit summaries.

Early termination data will be summarised in the specific visit where occurred.

Listings will include all scheduled, unscheduled and early discontinuation data.

6.2. BASELINE

The Screening/Baseline Period is defined as the period from informed consent signature to the first investigational study drug administration (i.e. C1D1 in **Parts A and B**). In the case where the last non-missing measurement and the reference start date coincide, that measurement will be considered pre-baseline (i.e. C1D1), but Adverse Events (AEs) and medications commencing on the reference start date will be considered post-baseline.

Baseline, is defined as the last scheduled non-missing measurement taken prior to dosing and will correspond to Day 1 (i.e. C1D1 in **Parts A and B**) for clinical laboratory evaluations and physical examinations and to Day 1, predose for PK concentrations, PD assessments vital signs and ECGs. However, if a patient is missing the planned baseline collection, the previous non-missing evaluation will become the baseline value.

The Baseline descriptive analysis will be based on the SAF set.

Document: PPD

Author: PPD

Version Number:

V2.2

Version Date:

21 March 2018

Template No: CS_TP_BS016 – Revision 3

Reference: CS_WI_BS005

Effective Date: 01May2012

Copyright © 2012 Quintiles Transnational Corp. All rights reserved.

The contents of this document are confidential and proprietary to Quintiles Transnational Corp. Unauthorized use, disclosure or reproduction is strictly prohibited.

6.3. RETESTS, UNSCHEDULED VISITS AND EARLY TERMINATION DATA

In general, for by-visit summaries, data recorded at the nominal visit will be presented.

Unscheduled safety measurements (Laboratory, Vital signs, ECG) of all patients, within each dose level for **Part A** and within MTD, for **Part B**, will be evaluated as following:

- if a planned visit was not performed, the nearest (± 3 days) unscheduled visit will be considered as the correspondent planned one.
- if unscheduled visits were performed in addition of the planned one, each unscheduled visit between two planned ones will be summarized and ordered by date.

In the case of a retest (same visit number assigned) of a non laboratory data (i.e. 3 ECG repeated as per QTc prolongation), the average of all measurements will be used for by-visit summaries.

Early termination data will be summarised in the specific visit where occurred.

Listings will include all scheduled, unscheduled and early discontinuation data.

